Frequent Standardized Oral Care to Improve
Health Outcomes in Premature Infants in the
Neonatal Intensive Care Unit

NCT # 06000761

8/23/2023

Protocol

1. **Project Title:** Frequent Standardized Oral Care to Improve Health Outcomes in Premature Infants in the Neonatal Intensive Care Unit

2. **Principal Investigators:** [name] PhD

3. **Abstract:**

Premature very low birth weight (VLBW) infants are susceptible to complications related to infrequent and non-standardized oral care. Although the benefits of frequent standardized oral care are known to reduce oral dysbiosis (increased level of potentially pathogenic bacteria) and its associated complications in critically ill adults leading to established evidence-based guidelines, no such information exists for VLBW infants. Premature VLBW infants are highly susceptible to costly, life threatening and potentially preventable morbidities, such as ventilator associated pneumonia (VAP), bronchopulmonary dysplasia (BPD; oxygen requirement at 28 days of life), and need for prolonged respiratory support which require additional treatments, increase cost of care, and can lead to chronic illness, re-hospitalization, and developmental delay.^{1,2} A dearth of information exists regarding oral care in VLBW infants and no such guidelines exist for infants admitted to the neonatal intensive care unit (NICU) which may negatively affect their health. Thus, research regarding the effect of frequent, standardized oral care on the health of VLBW infants is essential to develop guidelines thus potentially improving the health of this vulnerable population. If successful, this research could change practice in NICUs across the nation.

4. **Background:**

VLBW infants are at significant risk of adverse health outcomes including ventilator associated pneumonia, bronchopulmonary dysplasia, and prolonged respiratory support which increase costs and are associated with chronic illness, re-hospitalization, and developmental delay. The oral cavity of patients admitted to intensive care units contains high levels of pathogenic bacteria which can be aspirated, inhaled and invade the systemic, respiratory and gastrointestinal systems increasing the risk of adverse health outcomes. Extensive research regarding the benefits of oral care in critically ill adults has led to nationally recognized evidence-based guidelines.

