1. Using a sponge-tipped swab saturated with sterile water or human milk, the bedside nurse or research coordinator (with extensive NICU nursing experience) will clean all 4 quadrants of the gum surfaces and upper posterior part of the oropharynx for 15 seconds each.
2. Using a new sterile water or human milk saturated swab, they will clean the ventral and posterior surfaces of the tongue for 15 seconds.
3. Using a new sterile water or human milk saturated swab, they will gently clean the outer surface of the endotracheal tube (if present), feeding tube or other oral tubes.
4. The lips will be cleaned with a sterile gauze saturated with sterile water or human milk.
5. The oral cavity will be suctioned as needed with an oral suction device to remove secretions (oral suction devices are changed every 24 hours per NICU protocol).
6. After the above oral care is complete, 0.1 mL of mom's breast milk will be placed into each buccal cavity (if available) until reaching day of life #7, if infant meets the NICU policy of a birth weight of \leq 1250 grams. Orally administered breast milk is routine nursing care for premature infants in this NICU and may interact with the oral lymphoid tissue to help support immune system development.¹⁵

Aim 1 will determine the effect of standardized frequent oral care using human milk on the oral microbiome including bacterial pathogenicity determinants in premature VLBW infants. We hypothesize that standardized oral care performed every 3-4 hours using human milk will be associated with less dysbiosis than standardized oral care every 3-4 hours or 12 hours using sterile water. A sample of the infant's saliva will be collected weekly for 4 weeks by the research coordinator (a registered nurse experienced in the care of critically ill infants) by gently inserting a sterile brush into the infant's mouth and gently rotating the swab. Collection will occur immediately prior to the infant's scheduled oral care. Our team is skilled in the collection, processing and analysis of infant saliva.

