DNA Extraction & 16S rRNA sequencing. DNA will be extracted from saliva using PowerFecal DNA isolation kit (MO BIO Laboratories) and quantified using a Nanodrop spectrophotometer (Thermo Scientific, Wilmington, DE). V4 universal primers will be used for 16S rRNA amplification and subsequent Illumina MiSeq sequencing. Samples will be amplified in 25 μ l reactions containing 0.5 Units Phusion High-Fidelity Polymerase (New England Biolabs, Ipswich, MA), 1X Phusion HF Reaction Buffer, 0.75 μ l DMSO, and 0.2 mM each dNTP. Triplicate PCR amplifications will be pooled for each sample, and cleaned with a QIAquick PCR Purification kit (Qiagen). 200 nanograms of each cleaned amplicon library will be submitted for sequencing at the ICBR core facility at UF. Sequencing will be performed on an Illumina MiSeq with a 300-bp paired-end protocol, using single indexing.

Microbiome 16S rRNA Gene Analysis. Sequencing reads will be parsed by Illumina index at the sequencing center. Paired reads will be merged, and primers and adaptors will be removed using a combination of tools in cutadapt, Galaxy, and eutils. Sample names will be added to the definition lines of sequencing reads using sed and concatenated into one fasta file, to make them compatible for analysis in QIIME v1.9.¹⁶ Clustering of Operational Taxonomic Units (OTUs) at 97% similarity will be performed with the subsampled open-reference OTU picking method,¹⁷ with no removal of singletons. The Greengenes reference dataset version 13.8 will be used as the reference for OTU picking and for taxonomy assignment with uclust.¹⁸ Community structure will be analyzed in R with phyloseq and will be plotted with ggplot2. Analysis of similarities (ANOSIM) will be performed in R using VEGAN v2.0-8. Statistical significance of QIIME profiles will be assessed using STAMP for comparison of two independent groups. TIME will be utilized for analysis of the longitudinal microbiome data. These tests are appropriate for analysis between groups and over time.

Stool samples will be collected at the end of week 1 and 4 by the research nurse. Following collection, all samples will be placed in a sterile specimen container and immediately frozen at -80 degrees Celsius for later analysis for inflammatory markers and 16S rRNA sequencing.

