To determine bacteria in the infant's mouth which may originate from the mother's breast milk or donor milk, a small sample of breast milk (3-5 mL) will be obtained from the infant's mother (after her consent) at the end of week 1 and 4 and 16S rRNA sequencing will be performed. Samples will be obtained from the NICU milk room. If mother is pumping < 5mL/, no sample will be obtained but no deviation reported. If donor breast milk is used for oral care (mother is not providing breast milk to her infant), 3-5 mL of donor breast milk will be obtained and 16s rRNA sequencing performed

Aim 2: will compare respiratory outcomes including evidence of VAP (positive ETT culture, incidence of ventilator associated events), days on invasive and non-invasive respiratory support, and incidence of BPD between groups. We hypothesize that infants who undergo standardized oral care every 3-4 hours will have less VAP, require fewer days of respiratory support, and have less BPD than Group 2. Descriptive statistics, including confidence intervals, will be generated to describe the distribution of days of respiratory support in each group, and measures of effect size (Cohen's *f*) will be calculated from the between-subjects (Treatment Group, with 3 levels) general linear model (GLM). Incidence of occurrence for VAP and BPD will be described for each group using frequencies and percentages along with confidence intervals for the proportions. Effect sizes (Cohen's *w*) for each of those two outcome variables will be calculated from a 3 (Treatment) by 2 (Occurrence) contingency table.¹⁹

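### Aim 1 hypothesises less dysbiosis in Group 3, but the named community test has no direction, and the signed alternative has no pathogen set and can be diluted by milk reads

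*Protocol*

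**What the plan says.** The Aim 1 hypothesis (Protocol, section 6) is directional: oral care with human milk every 3-4 hours "will be associated with less dysbiosis than standardized oral care every 3-4 hours or 12 hours using sterile water". The Abstract explains the term as "oral dysbiosis (increased level of potentially pathogenic bacteria", and the Background treats gram-negative flora as the potentially pathogenic kind.

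The paragraph on 16S rRNA gene analysis names three tools for comparison between groups or over time. For the community as a whole it states: "Analysis of similarities (ANOSIM) will be performed in R using VEGAN v2.0-8". On individual taxa, the plan is worded as follows: "Statistical significance of QIIME profiles will be assessed using STAMP for comparison of two independent groups". A third tool, TIME, is assigned to the repeated weekly samples. The authors then give their own view of the set: "These tests are appropriate for analysis between groups and over time".

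Saliva is taken weekly for four weeks, just before scheduled oral care. Milk is sequenced at the end of weeks 1 and 4, with the purpose "To determine bacteria in the infant's mouth which may originate from the mother's breast milk or donor milk". Table 1 lists this milk analysis under covariates, and lists the quantity and kind of oral bacteria as the saliva variable. Step 6 of the procedure, common to all groups, gives the mother's milk into the cheeks up to day 7 where it is available and birth weight is 1250 g or less.

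**The concern.** The hypothesis has a direction and the named community test does not. ANOSIM can show that Group 3's oral community differs from a water group's. It cannot show which community holds more potential pathogens.

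The treatment can also enter the assay. Only Group 3 has gums, tongue, lips and tubes swabbed with milk every 3-4 hours for four weeks, and its saliva is taken about 3-4 hours after the last swab. 16S sequencing of saliva does not separate residual milk DNA from resident flora. The protocol foresees milk bacteria in the mouth and sequences milk for that reason, but none of the group comparisons it names uses those sequences.

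At stake is the reading of the main Aim 1 result. A significant community difference could be taken as support for milk care when it reflects harm, or only the milk itself.

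**Working it through.** The protocol gives no alpha, power or effect size for Aim 1, so there is no stated figure to reproduce. The logic was checked algebraically and by simulation.

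**1. ANOSIM has no sign.** R = (mean between-group rank − mean within-group rank) / (M/2), where M is the number of sample pairs. Exchanging the group labels leaves every pair between-group or within-group as before, so R cannot change. In one simulated data set R was 0.268 with either labelling.

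**2. A raw share is diluted by milk.** If milk supplies a fraction m of reads and the pathogen share of resident flora is p, the observed share is p × (1 − m). With p = 40% and m = 10%, this is 0.40 × 0.90 = 36%. The share falls by 4 points in the hypothesised direction with the flora unchanged.

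**3. Simulation.** From the protocol: 217 infants in three groups, 217/3 ≈ 72 per group. Assumed: 8 potentially pathogenic, 22 other oral and 6 milk taxa, with no overlap between milk and oral taxa; 2% milk reads in the water group; Bray-Curtis distances; 199 permutations; p < 0.05; 200 runs per scenario. A Welch t-test on the summed share of the 8 pathogenic taxa stands in for a signed, STAMP-type comparison. The milk-excluded share is the pathogen share among the 30 non-milk taxa.

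| Group 3 scenario | ANOSIM mean R | ANOSIM significant | Raw share difference | Raw significant | Milk-excluded difference | Milk-excluded significant |
|---|---|---|---|---|---|---|
| No difference (2% milk) | 0.001 | 2.5% | −0.001 | 7% | −0.001 | 7% |
| Milk only, 5% | 0.018 | 48% | −0.009 | 6% | −0.001 | 4% |
| Milk only, 10% | 0.082 | 100% | −0.022 | 21% | 0.000 | 4% |
| Milk only, 20% | 0.243 | 100% | −0.047 | 80% | +0.001 | 6% |
| Milk only, 30% | 0.408 | 100% | −0.075 | 99% | 0.000 | 6% |
| Pathogens down, 2% milk | 0.065 | 100% | −0.110 | 100% | −0.112 | 100% |
| Pathogens up, 2% milk | 0.064 | 99% | +0.113 | 100% | +0.116 | 100% |

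The raw differences agree with the formula in step 2. The resident pathogen share is 8/30 = 0.267, so at 20% milk the expected difference is 0.267 × (0.02 − 0.20) = −0.048, against −0.047 simulated.

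A separate simulation with 20 taxa and 60 runs gave the same picture. A fall in gram-negative share from 40% to 29% and a rise from 40% to 53% gave mean R of 0.046 and 0.052, significant in 93% and 98% of runs. Milk alone at 10% of reads was significant in 100%, against 7% with no milk.

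**The case against.** The strongest reply is that ANOSIM does not stand alone. STAMP follows in the next sentence and is signed taxon by taxon, taxonomy is assigned, and Table 1 records quantity and kind of oral bacteria. A reader might infer that nothing in Aim 1 has a direction, or that the hypothesis can be neither confirmed nor refuted. The documents do not support that. They also nowhere say that a significant ANOSIM will be read as less dysbiosis. Describing STAMP for two groups is not fatal either, since the hypothesis contains two pairwise contrasts. What remains is that no pathogen set is named for STAMP, and that it works on the relative abundances which milk dilutes.

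Second, a dysbiosis index and the handling of a covariate are often left to a statistical analysis plan, which is not at hand. That is fair for missing detail. But the protocol itself pairs a directional hypothesis with an unsigned test and declares its tests appropriate.

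Third, milk bacteria that settle in the mouth may be part of the effect under study, and sampling just before care leaves the longest available gap after the last swab. Both points stand. They argue for reporting results with and without milk taxa.

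Fourth, the size of carry-over is unknown. At 5% milk ANOSIM rejected in only about half of runs, and cheek milk up to day 7 in eligible infants of all groups narrows the week 1 contrast. This limits the carry-over argument. The missing sign needs no carry-over assumption.

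**Conclusion.** The point holds in a limited form. ANOSIM cannot support a claim of less dysbiosis, because benefit and harm of similar size give almost the same R (0.065 and 0.064), and milk taxa alone can make it significant. The signed tool in the plan has no pathogen set, and its relative abundances move in the hypothesised direction when milk reads are present. With unchanged resident flora, a raw pathogen share fell significantly in 21%, 80% and 99% of runs at 10%, 20% and 30% milk.

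These rates rest on an assumed milk share and on simulated milk taxa that do not overlap the oral ones. They illustrate the mechanism and do not predict this trial. A reader might infer that any positive Aim 1 result would be an artefact; the documents give no residual milk share from which to say so. The change should be made, since it is cheap and decides how Aim 1 can be read.

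**What to change.** - Keep ANOSIM as descriptive, and state that it is not evidence of less dysbiosis.
- Test the hypothesis with a signed measure: the summed share of a list of gram-negative or potentially pathogenic genera, fixed before unblinding. Report Group 3 minus Group 1 and Group 3 minus Group 2 with intervals.
- At weeks 1 and 4, also compute the pathogen share among taxa not found in milk. Apply one exclusion list, pooled from the milk samples, to all three groups.
- Claim less dysbiosis only if the raw and milk-excluded results agree in direction. Read the milk-excluded interval as well as its sign: under pure carry-over that difference centres on zero, so the sign could agree by chance.

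The cost is wording and some added analysis of sequences already planned. The taxon lists must be agreed in advance. The exclusion drops some true colonisers that came from milk, and any listed pathogen also found in milk, which is why the raw result stays alongside it. The pooled list is needed because some infants will have no milk sample, for example when the mother's pumped volume is low. Weeks 2 and 3 have no milk samples, so their raw results keep the dilution caveat.

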In a national survey of 129 neonatal nurses from 35 states, we found that while over 98% stated oral care was important for the health of VLBW infants, less than 37% felt their NICU adequately addressed oral care. In addition, tremendous variation existed in practices regarding oral care including the method, timing, equipment and whether or not oral care was even performed.

5. Specific Aims:

The long-term goal of this research is to improve short and long-term health outcomes for premature very low birth weight (VLBW; <1500 grams) infants by decreasing complications caused by lack of frequent standardized oral care.

Specific aims are as follows:

Aim 1: To compare the oral microbiome between groups including bacterial pathogenicity determinants.

Aim 2: To compare respiratory outcomes including the incidence of ventilator associated pneumonia, bronchopulmonary dysplasia and need for respiratory support between groups.

6. Research Plan:

Sample and Setting:

The proposed study will prospectively follow 217 VLBW infants and 217 mothers (dyad) for 4 weeks following birth (includes 69 previously enrolled mother/infant dyads). Infants will be randomized into 1 of 3 groups. Standardized oral care will be performed every 3-4 hours (Group 1) and every 12 hours (Group 2) using sterile water. Group 3 will have standardized oral care performed every 3-4 hours using human milk (mother's breast milk or donor breast milk). Mothers of multiples will also be potential subjects. UF NICU nursing staff will receive UF Qualtrics survey links to their UF email yearly. Survey responses are voluntary and anonymous and will include up to 225 RN responses.

Infants will be sampled by convenience from the NICU at UF Health Shands Children's Hospital. Approximately 150 premature VLBW infants are admitted to this NICU per year. Our consent rate in similar studies is > 60% which strongly suggests we will be able to recruit 217 infants and 217 mothers (dyad) over a 12-month period.

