The proposed randomized controlled pilot study will follow a prospective cohort (n=217) of racially and economically diverse premature VLBW male and female infants following birth. Infants will be randomly assigned to one of three groups using a randomized blocks approach as implemented in SAS PROC PLAN. A randomized blocks approach will ensure comparable treatment group sizes, and a priori assignment will reduce possibility of bias in treatment group assignment. All groups will receive standardized oral care for 4 weeks. Infants in Group 1 will have standardized oral care performed every 3-4 hours with sterile water (dependent on scheduled care times), infants in Group 2 will have standardized oral care performed every 12 hours with sterile water, and Group 3 will have standardized oral care performed every 3-4 hours (dependent on scheduled care times) with human milk. Groups were chosen based upon recommendations for adults (every 3-4 hours) and data regarding common practices of neonatal nurses obtained from our national survey (every 12 hours) and the benefits of placing drops of human milk into the oral cavity of preterm infants.

Inclusion criteria: 1) mothers who are ≥ 18 years of age, 2) infant (s), including multiples, born at ≤ 30 weeks, 3) infant with birth weight at ≤ 1500 grams

Exclusion criteria: 1) infants with born congenital anomalies of the face, lungs, or gastrointestinal system 2) infant not expected to live > 7 days following delivery

Informed consent will be will be obtained from the mother or father within 72 hours after birth at the infant's bedside or in the mother's hospital room.

Procedure:

Oral care will be performed in infants in Group 1 (every 3-4 hours) using sterile water, Group 2 (every 12 hours) using sterile water and Group 3 (every 3-4 hours) using human milk (if mother's breast milk, not available, donor breast milk will be used). The following procedure and a checklist to ensure treatment fidelity. Equipment will be easily accessible and provided in sterile pre-packaged kits at the infant's bedside. Study personnel involved with subjects will be unable to be blinded since information regarding oral care is visually obvious and recorded in the chart by nursing staff. However, those performing analysis of saliva and collecting data on respiratory outcomes will be blinded to the infant's designated group. Feeding tubes will be changed no less than every 7 days.

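### Aim 1 ties statistical significance to a two-group test, and no stated method compares the three arms using the four weekly saliva samples from each infant

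*Protocol*

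**What the plan says.** Section 5 of the protocol sets Aim 1: "To compare the oral microbiome between groups including bacterial pathogenicity determinants". Section 6 gives the design: "Infants will be randomly assigned to one of three groups using a randomized blocks approach as implemented in SAS PROC PLAN". The Aim 1 hypothesis is that the frequent schedule "using human milk will be associated with less dysbiosis than standardized oral care every 3-4 hours or 12 hours using sterile water", which means Group 3 against Group 1 and Group 3 against Group 2. On sampling, "saliva will be collected weekly for 4 weeks by the research coordinator".

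The Aim 1 paragraph on 16S rRNA gene analysis names three methods, each for a different task:

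- The test for significance is stated as: "Statistical significance of QIIME profiles will be assessed using STAMP for comparison of two independent groups".
- Just before it, after a sentence on community structure, comes: "Analysis of similarities (ANOSIM) will be performed in R using VEGAN v2.0-8".
- The repeated samples are covered in a separate sentence: "TIME will be utilized for analysis of the longitudinal microbiome data".

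The paragraph then closes with a general assurance: "These tests are appropriate for analysis between groups and over time". The STAMP sentence is the only one in Aim 1 that speaks of statistical significance. For Aim 2, by contrast, the same section writes the three arms into the analysis: a treatment factor with three levels in the linear model, and a 3 by 2 table for the incidence outcomes.

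**The concern.** The one sentence that decides significance is written for a design with two groups and no repeated measurements. This trial has three groups and about four correlated samples per infant. The text does not say which two groups STAMP compares, at which week, or how the third arm enters. ANOSIM is given no grouping factor and no handling of repeated samples. TIME is given no arm contrast.

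Aim 1 is one of only two aims. If its deciding comparison is unclear, the pair of arms and the week can be chosen after the data are seen, and a reader cannot tell which result tests the hypothesis. The closing sentence makes this a statement to correct rather than a gap, because it declares the named tests suitable for a task that none of them is assigned.

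**Working it through.** **Inputs from the protocol.** Three arms; 217 infants, so 217/3 = 72.3, or about 72 per arm if allocation is equal; four weekly saliva samples; two hypothesised contrasts. The protocol states no significance level, power or effect size for Aim 1, so there is no figure of its own to reproduce.

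**Step 1: the methods against the design.**

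| Method | Task given in the text | Compares three arms? | Uses an infant's repeated samples? |
|---|---|---|---|
| ANOSIM | community structure | grouping factor not stated | not stated |
| STAMP | statistical significance | two groups only | groups treated as independent; week not stated |
| TIME | longitudinal data | no arm contrast stated | yes, longitudinal use stated |

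No row answers both questions with a yes.

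**Step 2: error rate of two pairwise tests.** Assume 5% two-sided per test, with no adjustment.

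- If the two tests were independent: 1 - 0.95² = 9.75%.
- They share Group 3, so they are correlated. A simulation of 200,000 null trials with 72, 72 and 73 infants gives 8.9% for at least one false rejection and 0.9% for both.

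**Step 3: what the repeated samples could add (illustration only).** Assumptions not in the protocol: 72 per arm, complete samples, one continuous dysbiosis summary, equal correlation ρ between an infant's weeks, two-sided 5%. In units of the single-week SD, the variance of an infant's four-week mean is (1 + 3ρ)/4.

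- ρ = 0.1, 0.3, 0.5: variance 0.325, 0.475, 0.625; SD 0.570, 0.689, 0.791.
- Constant difference of 0.4 SD: standardised difference of the mean = 0.4/0.570, 0.4/0.689, 0.4/0.791 = 0.70, 0.58, 0.51, against 0.40 at one week.
- Difference growing 0.1, 0.2, 0.3, 0.4 SD: average 0.25, so 0.25/0.570, 0.25/0.689, 0.25/0.791 = 0.44, 0.36, 0.32, against 0.40 at week 4.

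Simulated power per contrast with Holm adjustment (40,000 trials per setting):

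| Pattern | Four-week mean, ρ = 0.1 / 0.3 / 0.5 | Single week (week 4) |
|---|---|---|
| Constant 0.4 SD | 98 / 92 / 82% | about 61% |
| Growing 0.1 to 0.4 SD | 70 / 51 / 40% | about 61% |

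Under the growing pattern the four-week mean does better only if 0.25/SD exceeds 0.40. That requires an SD below 0.625, so (1 + 3ρ)/4 < 0.39 and ρ below about 0.19. Under the null, Holm on infant means holds the family-wise error at 4.6 to 4.7%.

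**The case against.** The hypothesis is itself a pair of two-group comparisons, so a two-group test fits each contrast and is valid at any one week. The next sentence hands the longitudinal data to TIME, and nothing limits ANOSIM to two groups. Read as a set, the closing sentence may mean ANOSIM and STAMP between groups and TIME over time. The choice of week, pair and adjustment is commonly left to an analysis plan, which is not at hand, and the study calls itself a pilot.

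Much of this stands. A reader might infer any of three stronger points, and the protocol supports none of them:

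- *That the stated test is invalid.* It is not, if it is applied pairwise at one week.
- *That the weekly samples will be pooled as if independent, inflating the error.* The protocol nowhere says so, and no error rate should be attached to it.
- *That three of each infant's four samples are necessarily wasted.* The text never confines STAMP to one week, and a two-group test could be run on infant averages.

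Nor is a four-week average clearly the better choice. Step 6 of the oral care procedure gives infants of 1250 g or less in every arm mother's milk into the cheeks, if available, until day 7. That could blunt the Group 3 contrast in week 1, and a late-emerging difference favours week 4.

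What does not stand is that this is only missing detail. The protocol fixes a test for significance and declares it suitable, while for Aim 2 the same section writes out the three-arm structure.

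**Conclusion.** The concern holds in a limited form and should be fixed. The sentence on significance does not match a three-arm design with repeated sampling, and the closing sentence claims a suitability that the listed methods, as assigned, do not deliver.

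The firm part is textual and rests on no assumption. The one error rate worth quoting is about 9% for two unadjusted Group 3 contrasts, assuming 5% per test and a claim made if either is significant. If the hypothesis were accepted only when both contrasts are significant, that inflation would not arise, but the protocol does not state that rule. The power figures depend on an assumed effect size, correlation and time pattern. They show that the choice of contrast matters and must be made beforehand, not that one choice is right.

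**What to change.** Replace the two-group sentence with a three-arm comparison that treats the infant as the unit. One suitable form is a mixed model for a named dysbiosis summary, with arm, week, arm-by-week, a random infant effect and a family effect, since multiples are eligible. Name Group 3 against Group 1 and Group 3 against Group 2 as the two Holm-adjusted contrasts. The investigators should fix in advance whether these are averaged over the four weeks or taken at week 4, and report the other as secondary.

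For ANOSIM, either name one week or permute whole infants with all their samples. STAMP can stay for exploratory pairwise screening of taxa with false-discovery-rate control, and TIME for longitudinal description. Reword the closing suitability sentence to name the model as the between-arm test.

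The cost is a short passage of text, agreement on the dysbiosis summary, and a little more analysis code in R, which is already planned. No new samples are needed. The downside is fewer nominally significant results, and some loss of power if the timing chosen for the contrast does not match when the arms actually separate.
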